10.2.2 Liver safety monitoring

To ensure participant safety and enhance reliability in determining the hepatotoxic potential of an investigational drug, a standardized process for identification, monitoring and evaluation of liver events has to be followed.

Please refer to [Table 16-1](#) in [Appendix 2](#) for complete definitions of liver laboratory triggers.

Once a participant is exposed to study treatment, it is suggested that every liver event defined in [Table 16-1](#) should be followed up by the investigator or designated personnel at the trial site, as summarized below. Additional details on actions required in case of liver events are outlined in [Table 16-2](#). Repeat liver chemistry tests (i.e. ALT, AST, TBL, ALP and G-GT) to confirm elevation.

These liver chemistry repeats should be performed using the local laboratory used by the site. Repeated laboratory test results must be reported as appropriate.

- If the initial elevation is confirmed, close observation of the participant will be initiated, including consideration of treatment interruption if deemed appropriate.
- Discontinuation of the investigational drug (refer to the Discontinuation of study treatment section), if appropriate
- Causality assessment of the liver event
- Thorough follow-up of the liver event should include based on investigator's discretion:
 - serology tests, imaging and pathology assessments, hepatologist's consultancy; obtaining more detailed history of symptoms and prior or concurrent diseases, history of concomitant drug use, exclusion of underlying liver disease

All follow-up information and procedures performed must be recorded as appropriate in the CRF.

10.2.3 Renal safety monitoring

Once a participant is exposed to study treatment, the following two categories of abnormal renal laboratory alert values should be assessed during the study period:

- Serum creatinine increase $\geq 50\%$ compared to baseline during normal hydration status
- Any one of the following:
 - Urine protein-creatinine ratio (PCR) $\geq 1\text{g/g}$ or $\geq 100\text{ mg/mmol}$, OR
 - New onset dipstick proteinuria $\geq 3+$, OR
 - New onset dipstick hematuria $\geq 3+$ (after excluding menstruation, UTI, extreme exercise, or trauma)

Abnormal renal event findings must be confirmed after ≥ 24 hours but ≤ 5 days after first assessment.

Once a participant is exposed to study treatment, renal laboratory alerts or renal safety events should be monitored and followed up by the investigator or designated trial staff according to the local practice, guidance is summarized in [Table 16-4](#) in [Appendix 2](#).

10.2.4 Data Monitoring Committee

This study will include an internal data monitoring committee (DMC), which will function independently of all individuals associated with the conduct of this clinical trial, including the site investigators participating in the study. Specific details regarding composition, responsibilities, data monitoring and meeting frequency, documentation of DMC reports, minutes and recommendations will be described in a separate DMC charter.

11 Data Collection and Database management

11.1 Data collection

All data should be recorded, handled, and stored in a way that allows its accurate reporting, interpretation, and verification.

Designated investigator staff will enter the data required by the protocol and defined in the assessment schedule ([Table 8-1](#)) into the Electronic Case Report Forms (eCRF). The eCRFs have been built using fully validated secure web-enabled software that conforms to 21 CFR Part 11 requirements, Investigator site staff will not be given access to the EDC system until they have been trained. Automatic validation programs check for data discrepancies in the eCRFs, allow modification and/or verification of the entered data by the investigator staff.

The investigator/designee is responsible for assuring that the data (recorded on CRFs) (entered into eCRF) is complete, accurate, and that entry and updates are performed in a timely manner. The Investigator must certify that the data entered are complete and accurate.

This study may also incorporate electronic technology (eSource DDE) to capture source documents and source data electronically, consistent with final ([CDER 2013](#)) FDA guidance regarding electronic source and Regulations related to the maintenance of adequate participant case histories ([21 CFR 312.62\(b\)](#)).

A Novartis representative will review the protocol and data capture requirements (i.e. eSource DDE and/or eCRFs) with the investigators and their staff.

After final database lock, the investigator will receive copies of the participant data for archiving at the investigational site.

All data should be recorded, handled, and stored in a way that allows its accurate reporting, interpretation, and verification.

11.2 Database management and quality control

Novartis personnel will review the data entered by investigational staff for completeness and accuracy. Electronic data queries stating the nature of the problem and requesting clarification will be created for discrepancies and missing values and sent to the investigational site via the EDC system. Designated investigator site staff are required to respond promptly to queries and to make any necessary changes to the data.

Concomitant treatments and prior medications entered into the database will be coded using the World Health Organization (WHO) Drug Reference List, which employs the Anatomical Therapeutic Chemical classification system. Medical history/current medical conditions and adverse events will be coded using the Medical Dictionary for Regulatory Activities (MedDRA) terminology.

Dates of screenings, randomizations, screen failures, as well as randomization codes and data about all study treatment (s) dispensed to the participant will be tracked using an Interactive Response Technology (IRT). The system will be supplied by a vendor, who will also manage the database. The data will be sent electronically to Novartis/Sponsor (or a designated CRO) at specific timelines.

Each occurrence of a code break via IRT will be reported to the clinical team and monitor. The code break functionality will remain available until study shut down or upon request of Novartis/Sponsor.

11.3 Site monitoring

Before study initiation, at an initiation visit or at an investigator's meeting, a Novartis representative will review the protocol and data capture requirements (i.e. eSource DDE and/or CRFs) with the investigators and their staff. During the study, Novartis employs several methods of ensuring protocol and GCP compliance and the quality/integrity of the sites' data. The field monitor will check the completeness of participant records, the accuracy of data capture / data entry, the adherence to the protocol and to Good Clinical Practice, the progress of enrollment, and to ensure that study treatment is being stored, dispensed, and accounted for according to specifications. Key study personnel must be available to assist the field monitor in conducting these activities. Continuous monitoring of each site's data will be performed throughout the conduct of the study. Additionally, a central analytics organization may analyze data and identify risks and trends for site operational parameters, and provide reports to Novartis clinical teams to assist with trial oversight. The investigator must maintain source documents for each participant in the study, consisting of case and visit notes (hospital or clinic medical records) containing demographic and medical information, laboratory data, electrocardiograms, and the results of any other tests or assessments. All information on CRFs must be traceable to the respective source documents. The investigator must also keep the original informed consent form agreed by the participant and/or legal representative (a copy is given to the participant).

The investigator must give the monitor access to all relevant source documents to confirm their consistency with the data capture and/or data entry. Novartis monitoring standards require verification for the presence of all informed consents, adherence to the inclusion/exclusion criteria, documentation of SAEs, and of data that will be used for all primary variables. Additional checks of the consistency of the source data with the CRFs are performed according to the study-specific monitoring plan. No information in source documents about the identity of the participants will be disclosed.

12 Data analysis and statistical methods

The primary analysis time point is Day 15. The analyses of efficacy and safety described in this protocol will occur when all participants in the study have completed their final study visit at Day 40.

Unless otherwise specified, descriptive summaries for categorical data will include frequencies and percentages, and continuous data will be presented with mean, standard deviation, median, minimum, and maximum. For selected parameters, 25th and 75th percentiles may also be presented.

Differences, relative ratios (RR) or odds ratios (OR) for the comparisons between the two treatment arms will be presented with 2-sided 95% confidence interval (CI). P-values will be presented only if a formal hypothesis test is performed.

Any data analysis carried out independently by the investigator should be submitted to Novartis before publication or presentation.

12.1 Analysis sets

The Randomized Analysis Set (RAS) consists of all randomized participants regardless of receiving study treatment.

The Full Analysis Set (FAS) comprises all participant to whom study treatment has been assigned by randomization excluding mis-randomized participants. Mis-randomized participants are defined as cases where IRT contact is made by the Investigator/qualified site staff either prematurely or inappropriately prior to confirmation of the participant's final randomization eligibility and treatment is not administered to the participant. According to the intent to treat principle, participants will be analyzed according to the treatment they have been assigned to during the randomization procedure.

The Safety Set (SAF) includes all participants who received at least one dose of study treatment. Participants will be analyzed according to the study treatment received, where treatment received is defined as the randomized/assigned treatment if the participant took at least one dose of that treatment or the first treatment received if the randomized/assigned treatment was never received.

The analysis of the primary objective and all other efficacy variables will be performed on the FAS. The Safety Set will be used in the analysis of all safety variables.

12.2 Participant demographics and other baseline characteristics

Demographic and other baseline data including disease characteristics will be listed and summarized descriptively by treatment group for all study participants in the FAS and safety set. Participant demographic and baseline characteristics will include: age, sex, race, ethnicity, height, weight, BMI, oxygen saturation (SpO₂), duration of symptom onset to randomization, duration from hospital admission to randomization, SARS-COV-2-RNA/viral load PCR test result (negative/positive), COVID-19 abnormal chest x-ray at baseline consistent with COVID-19 (No/Yes), requiring oxygen at randomization (No/Yes), [REDACTED].

Categorical data will be presented as frequencies and percentages. For continuous data, mean, standard deviation, median, minimum, and maximum will be presented. For selected parameters, 25th and 75th percentiles will also be presented.

Protocol-solicited medical history will be summarized by treatment group.

12.3 Treatments

The Safety set will be used for the analyses below. Categorical data will be summarized as frequencies and percentages. For continuous data, mean, standard deviation, median, 25th and 75th percentiles, minimum, and maximum will be presented.

The duration of exposure in days to hydroxychloroquine, azithromycin, and placebo will be summarized by means of descriptive statistics using the safety set.

Concomitant medications and significant non-drug therapies prior to and after the start of the study treatment will be listed and summarized according to the Anatomical Therapeutic Chemical (ATC) classification system and preferred term, by treatment group.

12.4 Analysis of the primary endpoint(s)/estimand(s)

The primary analysis for this study will be conducted on the FAS using a treatment policy strategy.

12.4.1 Definition of primary estimand(s)

The primary objective of the study is to demonstrate in participants receiving best standard of care that the percentage who achieve clinical response with hydroxychloroquine or hydroxychloroquine plus azithromycin is superior to placebo by Day 15.

The primary efficacy estimand defined in [Section 2.1](#) incorporates as its endpoint clinical response by Day 15 defined for participants with a pre-morbid oxygen requirement as: Discharge (or ready to discharge as evidenced by normal body temperature and respiratory rate, and stable oxygen saturation on ambient air or ≤ 2 L supplemental oxygen) OR survival without need for mechanical ventilation. The clinical response endpoint for participants without a pre-morbid oxygen requirement is defined as: discharge (or ready for discharge) OR survival without need for mechanical ventilation or oxygen supplementation for the last 24 hours.

The components of clinical response will be derived from the disease status CRF that will be collected whenever there is a change in disease status ([Section 8.3.1](#)). Day 15 is the last study day where these criteria can be met. Study participants can meet the clinical response criteria prior to Day 15 if the criteria for discharge are met. Handling of missing data are provided in [Section 12.4.4](#).

12.4.2 Statistical model, hypothesis, and method of analysis

The numbers and percentages of responders will be summarized by treatment group. The difference in observed response rates between active treatment groups and placebo arms will be presented along with 95% confidence intervals. The statistical hypothesis tested for clinical response is that there is no difference in the proportion of participants achieving clinical response at Day 15 with hydroxychloroquine or hydroxychloroquine plus azithromycin plus versus placebo.

Let p_j denote the proportion of clinical responders at Day 15 for treatment groups j , $j = 0, 1, 2$ where

- 0 corresponds to placebo
- 1 corresponds to hydroxychloroquine plus azithromycin
- 2 corresponds to hydroxychloroquine

The following statistical hypotheses will be tested to address the primary efficacy objective:

$$H_1: \frac{P_1(1-P_0)}{P_0(1-P_1)} = 1, H_{A1}: \frac{P_1(1-P_0)}{P_0(1-P_1)} \neq 1$$

$$H_2: \frac{P_2(1-P_0)}{P_0(1-P_2)} = 1, H_{A2}: \frac{P_2(1-P_0)}{P_0(1-P_2)} \neq 1$$

In other words,

H_1 : hydroxychloroquine plus azithromycin is not different to placebo with respect to the likelihood of clinical response by Day 15

H₂: hydroxychloroquine is not different to placebo with respect to the likelihood of clinical response by Day 15

The primary efficacy endpoint of clinical response at Day 15 in the FAS will be evaluated using a logistic regression model with treatment group and whether or not supplemental oxygen is required at randomization as explanatory variables. Odds ratios will be computed for each of active treatment comparisons to placebo. Based on what data is available from the evolving COVID-19 literature, it is anticipated that hydroxychloroquine plus azithromycin will have a greater clinical response than hydroxychloroquine and thus each of the primary and secondary hypotheses will be tested first in a closed testing procedure in order to preserve familywise Type I error rate at 0.05 two-sided. Details of the closed testing procedure are provided in [Section 12.5](#).

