12.4.7 Supportive analyses

The primary efficacy endpoint will be evaluated with respect to the following subgroups

- Age (18-65, > 65 years)
- SpO₂ (≤94% > 94%)
- Requiring supplemental oxygen at the time of randomization (No/Yes)

The primary estimand will be applied here to each of these subgroups variables adding the subgroup variable and treatment group by subgroup interaction to the model to evaluate whether there is any association between the level of subgroup variable and treatment.

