12.8 Sample size calculation

12.8.1 Primary endpoint(s)

Assuming a true treatment difference in clinical response of 20% for hydroxychloroquine plus azithromycin plus SoC vs. placebo plus SoC, and an odds-ratio of at least 2.25, a sample size of 148 participants per treatment group (444 overall) provides at least 93% power that the primary analysis will be statistically significant at the two-sided 5% significance level. This holds for a variety of different assumptions with respect to treatment and clinical response rates.

These sample size assumptions were evaluated using East Version 6.4.

The sensitivity of different assumptions for clinical response rate for treatment and control groups and effect size on power are summarized in [Table 12-1](#).

Table 12-1 Sensitivity of sample size to different response rates for 148 participants per group (N=444) and treatment differences for level of significance alpha = 0.05

HCQ/HCQ plus AZ Response Rate (%)	Standard of care response rate	Odds Ratio	Treatment difference (%)	Power (%)
50	35	1.86	15	74

HCQ/HCQ plus AZ Response Rate (%)	Standard of care response rate	Odds Ratio	Treatment difference (%)	Power (%)
50	30	2.33	20	94
50	25	3.00	25	99
60	45	1.83	15	73
60	40	2.25	20	93
60	35	2.79	25	99
70	55	1.91	15	76
70	50	2.33	20	94
70	45	2.85	25	99

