2.3.2 Background and demographic characteristics

Participant demographic and baseline characteristics will include:

- Age
- Age categories (≤ 65 , > 65 years)
- Sex
- Race
- Ethnicity
- Height
- Weight

[figure not shown]
- BMI

Background disease characteristics will include:

- Oxygen saturation at baseline ($\leq 94\%$; $> 94\%$)
- Requiring supplemental oxygen at baseline (No/Yes)
- Supplemental Oxygen Flow rate (L/min) (see also [section 2.4.2.3](#))
- Number of days from onset of symptoms to first dose of study drug
- Number days from hospital admission to first dose of study drug
- Chest imaging (x-ray or CT scan) status at baseline (Normal/Abnormal/not available)
- Pre-morbid oxygen requirement (No/Yes)
- 
- Tachypnea (i.e. respiratory rate > 24 bpm) at baseline (No/Yes)

Comorbidities will include:

- Number of comorbidities (0,1 >1) , where comorbidities include the following list of solicited terms: Cerebrovascular disease, Chronic heart disease, Hypertension, Asthma, COPD, Chronic kidney disease, Malignant neoplasm, Diabetes.

Demographic and other baseline data will be summarized descriptively by treatment group for all study participants in the FAS.

Categorical data will be presented as frequencies and percentages. For continuous data, mean, standard deviation, median, minimum, and maximum will be presented. For selected parameters, 25th and 75th percentiles will also be presented.

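### The protocol's primary model adjusts only for oxygen at randomization; pre-specifying age, SpO2 and pre-morbid oxygen would be a modest efficiency gain, not a correction

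*Protocol*

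**What the plan says.** Protocol 12.4.2 specifies a logistic regression of Day 15 clinical response on "treatment group and whether or not supplemental oxygen is required at randomization as explanatory variables". Section 12.5 uses the same single covariate for viral clearance, and the non-parametric sensitivity analysis in 12.4.5 carries over the primary model's variables.

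Three other baseline variables are collected:

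- **Age** (8.2.2).
- **SpO2**, measured with the vital signs (8.4.2) and listed as a baseline characteristic (12.2).
- **Pre-morbid oxygen requirement** (8.3.1). SAP 2.3.2 also lists it as a background disease characteristic: "Pre-morbid oxygen requirement (No/Yes").

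Age and SpO2 enter a model only in the subgroup analyses of 12.4.7, each with its own treatment interaction. Pre-morbid oxygen enters no model, although it decides which definition of response applies (Table 2-1). Section 6.3.2 names no stratification factor.

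Sample size section 12.8.1 assumes a 20-point difference and "an odds-ratio of at least 2.25". It says that 148 per arm "provides at least 93% power" for a result "statistically significant at the two-sided 5% significance level". It does not invoke covariate adjustment.

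The SAP was reduced after the study was halted with 20 participants randomized, one of them mis-randomized. It reports number and percentage of responders (2.5.2) and fits no statistical model (5.4), yet section 4 records no change to the protocol's analyses.

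**The concern.** Adjusting a logistic model for baseline variables that predict the outcome raises the power of the treatment test. Where randomization is not stratified, it also corrects for chance imbalance in those variables. The protocol regards age and SpO2 as important enough for subgroup analysis but leaves them out of the main model.

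Pre-morbid oxygen has a separate claim. Participants with that requirement can respond by surviving unventilated. The others must also be off oxygen over the final 24 hours, unless discharged or ready for discharge. Oxygen at randomization does not stand in for this, because it pools long-term users with newly hypoxic participants who face the stricter rule.

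The margin matters most for hydroxychloroquine alone. The 20-point assumption is made for the combination, which 12.4.2 expects to do better. At 15 points Table 12-1 gives only 73% to 76% power. In 12.5 that comparison (H2) comes before both viral clearance hypotheses, so a failure there would stop the ordered sequence.

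**Working it through.** **1. Reproduce the stated power.** The inputs come from protocol 12.8.1: n = 148 per arm, two-sided alpha 0.05, and the Table 12-1 row "60 40 2.25 20 93" (active rate, control rate, odds ratio, difference, power). The pooled-variance two-proportion test without covariates has

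power = Φ[(|p1 − p0| − 1.96·SE0) / SE1], where SE0 = √(2·p̄(1 − p̄)/n) and SE1 = √((p1(1 − p1) + p0(1 − p0))/n).

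- 60% vs 40%: SE0 = √(0.50/148) = 0.0581 and SE1 = √(0.48/148) = 0.0569. Power = Φ[(0.20 − 0.1139)/0.0569] = Φ(1.51) = **93.5%**, against 93% stated. The unpooled version gives 94.0% and the Wald log-odds-ratio version 92.8%.
- 60% vs 45%: SE0 = √(0.49875/148) = 0.0581 and SE1 = √(0.4875/148) = 0.0574. Power = Φ(0.63) = **73.6%**, against 73% stated.

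All nine rows of Table 12-1 reproduce within one point, so the design does not depend on adjustment.

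**2. Effect of adding the three covariates.** The documents give no prognostic strengths or prevalences, so these are assumptions:

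- Half of participants are on oxygen, with odds ratio 2.0 for that term.
- SpO2 is correlated with oxygen use; age is independent of it.
- 5% have a pre-morbid oxygen requirement.
- Added effects, weak / moderate / strong: age 1.28 / 1.65 / 2.46 per SD; SpO2 1.22 / 1.49 / 2.01 per SD; pre-morbid oxygen 1.65 / 2.7 / 4.5.

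Each scenario has 4,000 simulated two-arm trials at 148 per arm, with the marginal response rates held fixed. The planned model has treatment and oxygen; the enlarged model adds all three variables.

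| Added prognostic strength | Power (%), 60% vs 40%, planned → enlarged | Change (points) | Power (%), 60% vs 45%, planned → enlarged | Change (points) | Median odds ratio, 60% vs 40%, planned → enlarged |
|---|---|---|---|---|---|
| None | 94.1 → 93.8 | −0.3 | 74.8 → 74.8 | 0.0 | 2.34 → 2.36 |
| Weak | 94.1 → 94.4 | +0.3 | 76.4 → 77.3 | +0.9 | 2.32 → 2.39 |
| Moderate | 94.6 → 96.2 | +1.6 | 76.3 → 78.9 | +2.6 | 2.38 → 2.61 |
| Strong | 94.4 → 97.6 | +3.2 | 76.7 → 84.2 | +7.5 | 2.41 → 3.06 |

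Monte Carlo error on each power is about 0.4 point at 20 points' difference and 0.7 point at 15. With no treatment effect, the enlarged model rejected in 5.1% to 5.6% of trials.

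**3. Conditional and marginal odds ratio.** H1 and H2 are written in arm-level proportions. At 60% vs 40% the marginal odds ratio is (0.60 × 0.60)/(0.40 × 0.40) = 2.25. The last column shows that the model's odds ratio is already somewhat larger with one covariate and moves further with four. The odds ratio is non-collapsible, so this is a change in what is estimated, not bias.

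**4. Viral clearance.** At the 80% vs 50% assumed in 12.8.2, unadjusted power is already 99.99%, which leaves nothing measurable to gain.

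**5. Pre-morbid oxygen alone.** With an assumed odds ratio of 2.7 at 60% vs 40% (3,000 trials), adding only this term moved power from 94.1% to 93.9% at 2% prevalence, 93.7% to 94.3% at 5%, and 94.1% to 94.3% at 10%. All are within simulation error. At 2% prevalence the term failed to converge in 14% of trials.

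**The case against.** The strongest reply is that nothing here is wrong. A pre-specified logistic model with one severity covariate is valid, its type I error does not depend on the omission, and the stated power reproduces without it. That stands, and it rules out reading the point as a flaw in the primary analysis or a shortfall in sample size.

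Other inferences a reader might draw also go too far:

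- **That the power is free.** The odds ratio changes meaning as covariates are added, and a rare pre-morbid category may not be estimable.
- **That the gain is large.** SpO2 overlaps with the oxygen term; section 1.2 itself defines severe disease by low SpO2 or need for oxygen. Section 8.4.2 does not say whether SpO2 is read on room air. A sizeable gain needs strong effects that the documents do not establish.
- **That viral clearance loses power too.** At its own planning assumption it does not. It could benefit only indirectly, through H2 in the testing order.
- **That omitting pre-morbid oxygen adds material noise.** The argument for the term rests on the endpoint definition; step 5 shows no detectable power gain at an odds ratio of 2.7.
- **That these factors are never examined.** Section 12.4.7 brings age and SpO2 into the model, though one at a time and with an interaction, which does not give an adjusted overall effect.

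Finally, the trial was halted and the SAP fits no model. In a simulation at 19 participants with assumed moderate effects, the full three-arm model could not be estimated in 91% of trials, and in 22% even without the pre-morbid term. That confines the point to the protocol model at its planned size.

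**Conclusion.** The point holds as a modest, optional efficiency improvement to the primary analysis in protocol 12.4.2 and its sensitivity analysis in 12.4.5, at 148 per arm. Depending on how prognostic the variables are, the change in power is about 0 to +3 points at the design effect and about 0 to +8 points at 60% vs 45%, with no material loss if they are not prognostic at all. These ranges rest on assumed effect sizes, an assumed 50% on oxygen and an assumed 5% with a pre-morbid requirement.

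Age is the safest addition: in these assumptions it does not overlap with the oxygen term, and it is continuous, so sparseness is not an issue. The case for pre-morbid oxygen is one of coherence with the endpoint more than of power.

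The documents do not support calling the planned model invalid or the trial underpowered because of it, nor adding a model to the halted trial's analysis. One inconsistency stands apart from all this: SAP section 4 reports no change to protocol-specified analyses, while SAP 5.4 drops the protocol's models.

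**What to change.** In protocol 12.4.2 and 12.4.5:

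- Add age as a continuous covariate alongside oxygen at randomization.
- Add baseline SpO2 and pre-morbid oxygen requirement, with a rule fixed in advance for dropping a sparse or non-estimable term (for example, based on counts pooled over arms). Define which SpO2 reading is used and how a missing covariate is handled.
- State whether the reported odds ratio is conditional on the covariates or standardized to the marginal odds ratio in which H1 and H2 are written.

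Section 12.5 need not change for power reasons. State that the enlarged model applies at the planned sample size and is not to be fitted to the roughly 19 evaluable participants (20 randomized less one mis-randomized), for whom the SAP's descriptive counts remain appropriate. In SAP section 4, record that the protocol's logistic and sensitivity models were dropped, so that it agrees with 5.4.

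The cost is a few lines of text and no new data collection. The downsides are small: a conditional odds ratio differs from the marginal one, and the pre-morbid term may have to be dropped if the category is rare.
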